6.14 Pharmacogenomic Analyses

Pharmacogenomic sampling data will be listed only. Future cross-study pharmacogenomic analyses will be described in a separate analysis plan.

6.15 Safety Analyses

Safety analyses will be presented by the treatment received for the Safety Population.

6.15.1 Adverse Events

AE analyses will be presented by the treatment received for the Safety Population. Tabulations will be presented overall and by SoC (Yes, No).

AEs will be collected from the time of informed consent through completion of the participant's last study visit.

A treatment emergent adverse event (TEAE) is defined as:

- Any AE that has an onset on or after the first dose of study drug through completion of the last study visit.
- Any pre-existing AE that has worsened in severity on or after the first dose of study drug through completion of the last study visit.

AEs occurring prior to first dose are considered non-treatment emergent and will be listed only.

The Investigator will determine the relationship of the AE to treatment (Related, Not Related). If an AE has missing relationship it is assumed to be related to the study drug for analysis purposes.

Severity of the AE will be graded using the Common Terminology Criteria for Adverse Events (CTCAE) grading system (Version 5.0): Grade 1 (Mild), Grade 2 (Moderate), Grade 3 (Severe), Grade 4 (Life-Threatening), Grade 5 (Fatal). Grade 3 (Severe) will be assumed for an AE with missing grade.

An overall summary of AEs (incidence and number of events) will be presented by treatment group and overall, for the following:

- Any AE
- TEAE
- TEAE Related to Study Drug

QMD [REDACTED]	[REDACTED]
Confidentiality Statement	
This document is the property of [REDACTED] and may not be duplicated, copied, altered or removed from company without prior approval from [REDACTED] or in compliance with [REDACTED].	

[REDACTED]

Controlled Quality Management Document		
	Sponsor:	Pliant Therapeutics Inc.
	Protocol Number:	PLN-74809-IPF-202
STATISTICAL ANALYSIS PLAN. PHASE 2-3-4		

- TEAE Related to a Study Procedure
- Serious TEAE
- Serious TEAE Related to Study Drug
- TEAE of CTCAE Grade 3 or Higher
- TEAE of CTCAE Grade 3 or Higher Related to Study Drug
- TEAE Leading to Interruption of Study Drug
- TEAE Leading to Withdrawal of Study Drug
- TEAE Leading to Early Termination from Study
- TEAE Leading to Death

Summaries of TEAEs (incidence and number of events) will be presented by SOC and PT, by treatment group and overall, for the following:

- TEAE
- TEAE Related to Study Drug
- Serious TEAE
- Serious TEAE Related to Study Drug
- TEAE Related to a Study Procedure
- TEAE of CTCAE Grade 3 or Higher
- TEAE of CTCAE Grade 3 or Higher Related to Study Drug
- TEAE Leading to Interruption of Study Drug
- TEAE by SOC, PT and Maximum Grade (incidence only)

[REDACTED]

The following listings of TEAEs will be presented in Section 14.3.2 of the CSR.

- TEAE Leading to Withdrawal of Study Drug
- TEAE Leading to Early Termination from Study
- TEAE Leading to Death
- Serious TEAE

In addition, listings of all reported AEs and SAEs will be provided in Appendix 16.2.7 of the CSR.

[REDACTED]

QMD		
Confidentiality Statement		
This document is the property of [REDACTED] and may not be duplicated, copied, altered or removed from company without prior approval from [REDACTED] or in compliance with [REDACTED].		

[REDACTED]

Controlled Quality Management Document	
	Sponsor: Pliant Therapeutics Inc.
	Protocol Number: PLN-74809-IPF-202
STATISTICAL ANALYSIS PLAN. PHASE 2-3-4	

System organ class will be presented in descending order of frequency in the pooled PLN-74809 group and then alphabetically. Preferred terms will be displayed in descending order of frequency in the pooled PLN-74809 group and then alphabetically.

For summary by severity, patients reporting more than one AE per system organ class and preferred term will only be counted once for the most severe event.

6.15.2 Laboratory Data

Descriptive statistics of the observed values and change from baseline will be presented by treatment group and visit for each continuous hematology, serum chemistry, coagulation, and urinalysis parameter. Shift tables for the change from baseline in categorical parameters will be presented in the natural order of the outcome where possible.

Summaries and listings will be presented using the Système International (SI) unit for each parameter as received from the analytical laboratory.

Each measurement (for continuous data and for categorical data where provided) will be classed as below, within, or above normal range, based on ranges supplied by the laboratory used. Shift tables in relation to the normal range from baseline to each follow-up visit will be presented.

In addition, any confirmed liver abnormalities, identified per Section 6.2.19, will be summarized by treatment group and listed.

All individual laboratory data (including pregnancy testing data) will be listed. Any liver abnormalities identified will be provided as a separate listing.

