In Part D, participants will return to the study site for on-treatment evaluations on Day 1 and at Weeks 2, 4, 8, 12, 14, 20, 24, 26, and every 8 weeks after Week 24 until the last participant enrolled in Part D has completed this Week 24 visit. At this time, all participants will be contacted to return and complete the Final On-Treatment Visit (see Schedule of Events in [Appendix 2](#)). Blood and urine specimens for safety laboratory assessments will be collected after at least an 8-hour fast. A final study visit will be conducted 2 weeks \pm 3 days after the last dose of study drug (Week 14 \pm 3 days for Parts B and C; 2 weeks after the final On-Treatment Visit [\pm 3 days] for Part D), when participants will undergo a final [REDACTED] measurement, as well as follow-up end of study (EoS) evaluations.

Participants who discontinue study drug for safety reasons prior to completion of 12 weeks (Parts B and C) or at least 24 weeks (Part D) of treatment will be asked to remain in the study to complete all remaining assessments; if this is not feasible, they will be asked to return to the clinic for an Early Termination (ET) visit for follow-up evaluations.

[REDACTED] measurements will be obtained via spirometry and will be performed using study-standardized equipment and according to international guidelines (American Thoracic Society [ATS]/ European Respiratory Society [ERS]/ Japanese Respiratory Society [JRS]/ Latin American Respiratory Society [ALAT]). Spirometry reading will be centralized.

[REDACTED]
[REDACTED]
The DSMB will assess participant safety at predetermined intervals during the study, including prior to initiating Part D and following the enrollment of the last participant in Part D. [REDACTED]
[REDACTED]

The total number of participants enrolled in Parts B, C, and D of the study will be approximately 112, with approximately 84 receiving PLN-74809 and 28 receiving placebo.

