APPENDIX 1 SCHEDULE OF EVENTS: PARTS B AND C

	Screening	Treatment					EoS / ET
	Visit 1	Visit 2	Visit 3	Visit 4	Visit 5	Visit 6	Visit 7
	Day -28 to Day -1	Baseline Day 1	Week 2 Day 14 (±2 days)	Week 4 Day 28 (±2 days)	Week 8 Day 56 (±3 days)	Week 12 Day 84 (±3 days)	Week 14 Day 98 (±3 days)
Informed consent	X						
Medical history	X						
Demographics (age, sex, race)	X						
██████████	■					■	
Serum pregnancy test	X						
Check inclusion and exclusion criteria	X	X					
Complete physical examination (including height and weight)	X						
Targeted physical examination		X	X	X	X	X	X
Randomization		X					
██████	■	■		■	■	■	■
██████	■						
DLco	X						
██████████	■	■	■	■	■	■	■
Vital signs (post 3 minutes, supine; approx 2 hrs post dose and around the time of the █████)	X	X	X	X	X	X	X
██ ██	■	■	■	■	■	■	■
Hematology (post 8-hour fast)	X	X	X	X	X	X	X
Clinical chemistry (post 8-hour fast) ^f	X	X	X	X	X	X	X
Coagulation (post 8-hour fast)	X	X	X	X	X	X	X
Pharmacokinetic sample plasma × 2 (predose and at least 2 hours postdose) ^g		X		X		X	X ^g
Pharmacokinetic nintedanib/pirfenidone sample plasma x 2 (predose and at least 2 hours post dose to PLN-74809) ^h		X		X		X	X

- [REDACTED]
- g [REDACTED] PLN-74809 levels will be measured. Actual PK sample collection time and dosing time will be recorded. If the participant discontinues the study early, a plasma sample for PK should be taken at the ET Visit if possible.
- h For participants receiving nintedanib/pirfenidone only; timed relative to PLN-74809 dosing.

Week 14 Visit through End of Study

(continued)	Treatment							EoS / ET	
	Visit 7	Visit 8	Visit 9	Visit 10	Visit 11 ^a	Visit 12 ^a	Week 48 / Unscheduled / End of Treatment Visit EoT ^{a,b}	End of Study Visit EoS	
	Week 14 Day 98 (±3 days)	Week 20 Day 140 (±3 days)	Week 24 Day 168 (±3 days)	Week 26 Day 182 (±3 days)	Week 32 Day 224 (±5 days)	Week 40 Day 280 (±5 days)	Final On- Treatment Visit	Final On- Treatment Visit + 2 weeks (±3 days)	
██████████			■						
Targeted physical examination	X	X	X	X	X	X	X	X	
██████	■	■	■	■	■	■	■	■	
██████████	■	■	■	■	■	■	■	■	
Vital signs (post 3 minutes, supine; approx 2 hrs post dose and around the time of the █████)	X	X	X	X	X	X	X	X	
██ ██ ██████	■	■	■	■	■	■	■	■	
Hematology (post 8-hour fast)	X	X	X	X	X	X	X	X	
Clinical chemistry (post 8-hour fast) ^h	X	X	X	X	X	X	X	X	
Coagulation (post 8-hour fast)	X	X	X	X	X	X	X	X	
Pharmacokinetic sample plasma × 2 (predose and at least 2 hours postdose) ^{f, i}			X						

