1 INTRODUCTION

This document details the planned statistical analyses for Pliant Therapeutics Inc., protocol number “PLN-74809-IPF-202” study titled “A randomized, double-blind, dose-ranging, placebo-controlled Phase 2a evaluation of the safety, tolerability, and pharmacokinetics of PLN-74809 in participants with idiopathic pulmonary fibrosis (IPF) (INTEGRIS-IPF)”.

The proposed analyses are based on the contents of Protocol Amendment 3, dated 19 October 2021.

This is a Phase 2a, multicenter, 4-part, randomized, double-blind, dose-ranging, placebo-controlled study to evaluate the safety, tolerability, and pharmacokinetics (PK) of once-daily (QD) treatment with PLN-74809 in participants with idiopathic pulmonary fibrosis (IPF).

Each study part consists of an up to 28-day screening period, a 4-week (Part A), 12-week (Parts B and C), or at least 24-week (Part D) treatment period, and a 2-week (±3 days) post-treatment follow-up period.

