6 PLANNED ANALYSES

Any statistical analysis plan (SAP) prepared in advance of final participant data cannot be definitive, therefore the Clinical Study Report (CSR) may contain additional tables or statistical tests if warranted by the data obtained. The justification for any such additional analyses will be fully documented in the final CSR.

Please note: Since study Part A is considered complete, data from the one enrolled participant in Part A will be listed only. Analyses described herein refer to analysis of data from participants taking part in study parts B, C, and D only.

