6.15.3 Vital Signs

Descriptive statistics for observed values and changes from baseline in the following vital signs will be presented by treatment group at each visit:

- Systolic blood pressure (mmHg)
- Diastolic blood pressure (mmHg)
- Pulse rate (bpm)
- Respiration rate (breath/min)
- Body temperature (degrees Celsius)
- Body weight (kg)

Confidentiality Statement	
This document is the property of [REDACTED] and may not be duplicated, copied, altered or removed from company without prior approval from [REDACTED] or in compliance with [REDACTED].	

Controlled Quality Management Document		
	Sponsor:	Pliant Therapeutics Inc.
	Protocol Number:	PLN-74809-IPF-202
STATISTICAL ANALYSIS PLAN. PHASE 2-3-4		

follow-up visit will be tabulated by treatment group. All data, including details of clinically significant findings will be listed.

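### Could the Week 14 row of the laboratory and vital-sign tables show a false dose step, because 320 mg is on drug and the lower doses are off it?

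*SAP*

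**What the plan says.** SAP Section 6 covers the three later parts together: "Analyses described herein refer to analysis of data from participants taking part in study parts B, C, and D only". For laboratory data, Section 6.15.2 states that "observed values and change from baseline will be presented by treatment group and visit for each continuous hematology, serum chemistry, coagulation, and urinalysis parameter", and adds: "Shift tables in relation to the normal range from baseline to each follow-up visit will be presented". Section 6.15.3 provides for descriptive statistics "in the following vital signs will be presented by treatment group at each visit". Section 6.2.8 limits the tables to scheduled post-baseline values, and Section 6.2.4 leaves early-termination assessments out of the summaries. Section 6.3.6 places the four doses and placebo side by side.

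The protocol gives Week 14 two meanings. In Section 3.1, the final visit of Parts B and C comes two weeks (give or take three days) "after the last dose of study drug (Week 14" in the protocol's own parenthesis. Part D instead has "on-treatment evaluations on Day 1 and at Weeks 2, 4, 8, 12, 14, 20, 24, 26, and every 8 weeks after Week 24". Appendices 1 and 2 both number this visit 7 and place it at Day 98. Appendix 1 heads it as end of study or early termination; Appendix 2 puts it under treatment. Hematology, chemistry, coagulation and vital signs are marked at the visit in both.

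**The concern.** Visit number, week and study day all coincide, so a table keyed on any of them merges two drug states. The only dose still on drug at that point is also the highest, so recovery after stopping the lower doses would mimic a dose response. Safety and tolerability are the primary objective, the study is dose-ranging, and Protocol 3.2 says that its findings will inform later dose selection. A reader scanning the Week 14 row could conclude that a laboratory change belongs to 320 mg when it had been present at every dose and had simply faded.

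No legible rule for these tables separates visits on treatment from visits after treatment. The word follow-up does not help. In SAP Section 1 it names the "post-treatment follow-up period", while in Section 6.15.2 it reads as any visit after baseline.

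**Working it through.** **Planned numbers.** These come from Protocol 6.4 and the randomization ratios.

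- 40 mg: 28 × 3/4 = 21
- 80 mg and 160 mg: 56 × 3/8 = 21 each
- 320 mg: 28 × 3/4 = 21
- Placebo: 28/4 + 56 × 2/8 + 28/4 = 7 + 14 + 7 = 28

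This reproduces the stated 21 per dose (Protocol 12.2) and the stated 84 active and 28 placebo (Protocol 3.1). A merged Week 14 row would hold 3 × 21 = 63 active participants off drug and 21 on drug. The 63 would be 14 − 3 = 11 to 14 + 3 = 17 days past the last dose.

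**Size of a false step.** Let every dose have the same on-drug mean shift d, and let a share r of it fade in two weeks. The documents give neither value. The lower doses then show (1 − r)d and 320 mg shows d, so the step is r × d. The standard error of a difference between two groups of 21 is SD × √(2/21) = 0.309 SD. With d = 0.5 SD assumed:

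| r | step (SD) | step / SE | chance that 320 mg ranks highest of four doses |
|---|---|---|---|
| 0 | 0 | 0 | 25% |
| 0.25 | 0.125 | 0.41 | 42% |
| 0.5 | 0.25 | 0.81 | 60% |
| 1.0 | 0.5 | 1.62 | 88% |

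The last column takes normal means with 21 per dose.

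For the shift tables, assume that 20% of participants move out of range on drug. At 320 mg, 0.20 × 21 = 4.2 are expected. If the whole 20% is due to drug, each lower dose shows 4.2 × (1 − r) = 3.2, 2.1 or 0 for r = 0.25, 0.5 or 1. If half is background, each lower dose shows 21 × (0.10 + 0.10(1 − r)) = 3.7, 3.2 or 2.1, which halves every gap.

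These figures are upper bounds for the chosen d and r. Protocol 3.1 asks participants who stop drug for safety reasons to complete the remaining assessments, so the 320 mg column can itself contain people off drug at Week 14. If a share s of that arm has stopped and lost the same share r of its shift, the step falls to r × d × (1 − s).

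**Whether such a row would be built.** SAP 6.15.2 and 6.15.3 say visit; they do not say week or visit number. Part D's end-of-study visit comes two weeks after a final on-treatment visit whose timing depends on enrolment. With 24 to 48 weeks of treatment (Protocol 3.3), it falls between about Week 24 + 2 = 26 and Week 48 + 2 = 50. In Appendix 2 that column carries no visit number. Neither a week key nor a number key can place Part D's end-of-study data, so a combined table needs a row named for that visit. The Parts B/C Visit 7 already bears that name in Appendix 1.

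Section 6.2.4 points the same way. Appendix 1 uses one column for end of study and early termination, and only the latter is dropped from summaries. The programmer must therefore identify the visit by type.

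**Where the rule would sit.** SAP 6.3.2 puts dataset specifications in a separate document. Section 6.3.3 checks outputs against an agreed shell template. Visit mapping and row labels ordinarily live there. The SAP's table list is blacked out, and the text after the vital-sign list is incomplete, so their silence is no evidence of a missing rule.

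**The case for a change.** The strongest case for a change is that nothing legible prevents the merged row. Sections 6.2.4 and 6.2.8 remove early-termination and unscheduled values, but a completer's Week 14 visit in Parts B/C is neither. The Part D interim stops at Week 12, which protects the interim but not the final combined tables. A mapping sentence would cost almost nothing.

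The facts in that case stand: the two visits share a label, and a row built on that label would mislead for any effect that reverses in two weeks. It does not stand that the plan calls for such a row.

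The fuller remedy, restricting Part D Week 14 to its own placebo group, would also go further than the problem. Placebo has no drug effect to lose, so the comparator does not create the dose step. Cutting placebo from 28 to 7 raises the standard error of 320 mg minus placebo from √(1/21 + 1/28) = 0.289 SD to √(1/21 + 1/7) = 0.436 SD, a ratio of 1.51. Naming the Parts B/C visit as end of study removes the mixing without that loss.

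**Conclusion.** No change to the plan. This is an unwritten mapping rule that analysts would ordinarily fill sensibly, by showing the Parts B/C Week 14 visit as end of study, two weeks after the last dose, apart from Part D Week 14 on treatment. Confirming that label belongs to the routine check of the table shells.

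If the rows were nevertheless keyed on week, the harm would be confined to one row of the final laboratory and vital-sign tables. SAP 3.1 lists these as other safety endpoints, the summaries are descriptive, and Protocol 12.1 states that no hypotheses are tested. The Week 12 row, where every dose is scheduled on drug, would not show the step. For an assumed equal shift of 0.5 SD the step runs from nothing to 0.5 SD (0 to 1.62 standard errors), depending entirely on how much fades in two weeks. That range rests on assumed values and takes every 320 mg participant as still on drug. The conclusion about row labels is an inference from how the two schedules name their visits, because the shells cannot be seen.

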6.15.3 Vital Signs

Descriptive statistics for observed values and changes from baseline in the following vital signs will be presented by treatment group at each visit:

- Systolic blood pressure (mmHg)
- Diastolic blood pressure (mmHg)
- Pulse rate (bpm)
- Respiration rate (breath/min)
- Body temperature (degrees Celsius)
- Body weight (kg)

Confidentiality Statement	
This document is the property of [REDACTED] and may not be duplicated, copied, altered or removed from company without prior approval from [REDACTED] or in compliance with [REDACTED].	

Controlled Quality Management Document		
	Sponsor:	Pliant Therapeutics Inc.
	Protocol Number:	PLN-74809-IPF-202
STATISTICAL ANALYSIS PLAN. PHASE 2-3-4		

follow-up visit will be tabulated by treatment group. All data, including details of clinically significant findings will be listed.

7 INTERIM ANALYSIS

Interim analyses will be conducted at the following milestones:

- Upon completion of Parts B and C (following full enrollment and 12-week treatment duration with 40, 80, or 160 mg PLN-74809).
- Upon completion of 12-week treatment duration with 320 mg PLN-74809 in Part D.

A database freeze will occur upon completion of study Part C by the last participant. All data for study part A, B and C will be 100% cleaned and signed off by the investigators. After database freeze, participants will be unblinded and these data will be used for the statistical analysis and reporting of Parts A, B and C.

Blinding measures for interim analyses performed on data up to Week 12 for all participants in Part D will be described in a separate blinding plan.

Interim data from Part D will include all assessments up to the Week 12 assessments, [REDACTED] Adverse events or concomitant medications started/initiated post Day [REDACTED] will not be summarized in the in the interim analysis and will be presented in the final analysis. Participants who discontinue treatment or the study post the Week 12 assessment date up to Day [REDACTED] will be summarized as on treatment/on study for the purposes of the interim analyses.

8 DATA SAFETY MONITORING BOARD ANALYSIS

Data Safety Monitoring Board (DSMB) analyses [REDACTED] will be performed by an external vendor.

9 CHANGES TO PLANNED PROTOCOL ANALYSIS

1. Adverse event summaries and efficacy assessments will be presented overall and [REDACTED]
2. Change from Baseline at Week 12 in efficacy assessments will also be presented by [REDACTED]

QMD [REDACTED]	
Confidentiality Statement	
This document is the property of [REDACTED] and may not be duplicated, copied, altered or removed from company without prior approval from [REDACTED] or in compliance with [REDACTED].	

Controlled Quality Management Document		
	Sponsor:	Pliant Therapeutics Inc.
	Protocol Number:	PLN-74809-IPF-202
STATISTICAL ANALYSIS PLAN. PHASE 2-3-4		

3. [REDACTED]
4. A mixed model for repeated measures [REDACTED].
5. Definition of Efficacy Per Protocol Population was revised from:
[REDACTED]
6. Removed CTCAE grading summaries for laboratory test parameters.
[REDACTED]
8. Added additional pooled placebo groups for comparison purposes.

11 LIST OF TABLES, FIGURES AND LISTINGS

The following table includes details of the tables, figures, and listings to be included within each section of the electronic common technical document (eCTD). The eCTD section is shown in bold.

Number	Title	Population

Confidentiality Statement

This document is the property of [REDACTED] and may not be duplicated, copied, altered or removed from company without prior approval from [REDACTED] or in compliance with [REDACTED]

Controlled Quality Management Document	
Sponsor:	Pliant Therapeutics Inc.
Protocol Number:	PLN-74809-IPF-202
STATISTICAL ANALYSIS PLAN. PHASE 2-3-4	

Number	Title	Population
[Redacted Table Content]		

Confidentiality Statement

This document is the property of [Redacted] and may not be duplicated, copied, altered or removed from company without prior approval from [Redacted] or in compliance with [Redacted]

[REDACTED]		Controlled Quality Management Document	
[REDACTED]	[REDACTED]	Sponsor:	Pliant Therapeutics Inc.
[REDACTED]	[REDACTED]	Protocol Number:	PLN-74809-IPF-202
STATISTICAL ANALYSIS PLAN. PHASE 2-3-4			

Number	Title	Population
[REDACTED]	[REDACTED]	[REDACTED]
[REDACTED]	[REDACTED]	[REDACTED]
[REDACTED]	[REDACTED]	[REDACTED]
[REDACTED]	[REDACTED]	[REDACTED]
[REDACTED]	[REDACTED]	[REDACTED]
[REDACTED]	[REDACTED]	[REDACTED]
[REDACTED]	[REDACTED]	[REDACTED]
[REDACTED]	[REDACTED]	[REDACTED]
[REDACTED]	[REDACTED]	[REDACTED]
[REDACTED]	[REDACTED]	[REDACTED]
[REDACTED]	[REDACTED]	[REDACTED]
[REDACTED]	[REDACTED]	[REDACTED]
[REDACTED]	[REDACTED]	[REDACTED]
[REDACTED]	[REDACTED]	[REDACTED]
[REDACTED]	[REDACTED]	[REDACTED]
[REDACTED]	[REDACTED]	[REDACTED]
[REDACTED]	[REDACTED]	[REDACTED]
[REDACTED]	[REDACTED]	[REDACTED]
[REDACTED]	[REDACTED]	[REDACTED]
[REDACTED]	[REDACTED]	[REDACTED]
[REDACTED]	[REDACTED]	[REDACTED]
[REDACTED]	[REDACTED]	[REDACTED]
[REDACTED]	[REDACTED]	[REDACTED]
[REDACTED]	[REDACTED]	[REDACTED]
[REDACTED]	[REDACTED]	[REDACTED]

Confidentiality Statement

This document is the property of [REDACTED] and may not be duplicated, copied, altered or removed from company without prior approval from [REDACTED] or in compliance with [REDACTED]

		Controlled Quality Management Document	
		Sponsor:	Pliant Therapeutics Inc.
		Protocol Number:	PLN-74809-IPF-202
STATISTICAL ANALYSIS PLAN. PHASE 2-3-4			

Number	Title	Population
[REDACTED]	[REDACTED]	[REDACTED]
[REDACTED]	[REDACTED]	[REDACTED]
[REDACTED]	[REDACTED]	[REDACTED]
[REDACTED]	[REDACTED]	[REDACTED]
[REDACTED]	[REDACTED]	[REDACTED]
[REDACTED]	[REDACTED]	[REDACTED]
[REDACTED]	[REDACTED]	[REDACTED]
[REDACTED]	[REDACTED]	[REDACTED]
[REDACTED]	[REDACTED]	[REDACTED]
[REDACTED]	[REDACTED]	[REDACTED]
[REDACTED]	[REDACTED]	[REDACTED]

Number	Title	Population
[REDACTED]	[REDACTED]	[REDACTED]

Confidentiality Statement

This document is the property of [REDACTED] and may not be duplicated, copied, altered or removed from company without prior approval from [REDACTED] or in compliance with [REDACTED]

Controlled Quality Management Document	
Sponsor:	Pliant Therapeutics Inc.
Protocol Number:	PLN-74809-IPF-202
STATISTICAL ANALYSIS PLAN. PHASE 2-3-4	

Number	Title	Population			

Confidentiality Statement

This document is the property of [REDACTED] and may not be duplicated, copied, altered or removed from company without prior approval from [REDACTED] or in compliance with [REDACTED]
